3.2 Study Objectives

The primary objective of the study will be:

1. To measure the effect of NR vs PBO on standard assessments of cognition and subjective cognitive concerns.

The secondary clinical objectives of the study will be:

- 2. To measure the effect of NR vs PBO on neuropsychiatric symptoms;
- 3. To measure the effect of NR vs PBO on physical functioning.

The tertiary clinical objective of the study will be:

1. To elucidate how NAD+ levels, cognitive functioning, neuropsychiatric and physical symptoms, and markers of neural injury and inflammation differ between individuals with long-COVID and healthy controls.

The exploratory biomarker objectives of the study will be:

- 1. To measure the effect of NR on plasma biomarkers of metabolic target engagement and central nervous system (CNS) neural and glial integrity measurable in blood.
- 2. To measure the effects of NR on cerebral neurophysiology (in an optional sub-study) using resting state functional magnetic resonance imaging (rs-fMRI). Connectivity will be measured with rsBOLD.

3.2.1 Standardized Cognitive, Functional, and Neuropsychiatric Outcome Measures

The primary outcome of this study will be objective measures of cognitive performance and subjective cognitive concerns measured with the following tests:

O The Mini-Mental State Examination (MMSE)²², Wechsler Adult Intelligence Scale-Fourth Edition (WAIS-IV) Digit Span backwards²³, Repeatable Battery for the Assessment of Neuropsychological Status (RBANS)²⁴, the Trail Making Test (TMT)²⁵, the Delis-Kaplan Executive Function System (DKEFS) Verbal Fluency²⁶, and the Continuous Performance Test (CPT). ²⁷ Subjective ratings of everyday cognitive functioning will be measured using items from the Behavior Rating Inventory of Executive Function (BRIEF-A)²⁸ at week 2, week 12 and week 22, and the Everyday Cognition scale (ECog)²⁹ will be measured at each visit.

The secondary and tertiary clinical and exploratory biomarker outcomes of this study will be:

• Assessment of neuropsychiatric symptoms as measured by:

Randomized, Placebo-Controlled Parallel Group Clinical Trial of Nicotinamide Riboside to evaluate NAD+ Levels in Individuals with Persistent Cognitive and Physical Symptoms After COVID19 Illness ("Long-COVID")

Version 1.1

- o Ratings of mood and anxiety will be measured using the Post Traumatic Stress Disorder Checklist-Civilian (PCL-C)³⁰, Beck Anxiety Inventory (BAI)³¹ and Beck Depression Inventory (BDI)³². These standard measures will be administered at each visit.
- Assessment of physical functioning as measured by:
 - o The Fatigue Severity Scale³³.
 - Objective daily physical activity levels and sleep data collected using wrist actigraphy (Fitbit Charge 4).
 - Subjective sleep ratings (Pittsburgh Sleep Quality Index)³⁴ and physical activity (International Physical Activity Questionnaire [IPAQ])³⁵ measures will be collected using questionnaires at each visit.
- Safety and tolerability will be assessed with adverse event (AE) reporting conducted at every visit.
- Plasma for biomarkers will be collected at Week 2, and at every 5 weeks until the end-of-study, and at the one-time visit for HC and long-covid participants. Plasma biomarkers assays will consist of ultrasensitive immunochemical measures of proteins reflecting neurodegeneration/neural injury (e.g. NfL, IL-6 and GFAP), as well as NAD+/NADH).
- Cerebral neurophysiology will be measured with functional MRI (optional sub-study).
 - Optional MRI will be conducted at two time points: Week 2 and End of Study (Week 22). Healthy controls will complete the MRI at their one-time visit. Each MRI scan session will include functional MRI with resting state BOLD (rs-fMRI) and pseudo-continuous arterial spin labeling (pCASL) sequences. rs-fMRI measures spontaneous yet synchronized fluctuations in the BOLD signal to determine the strength of functional connectivity within various intrinsic brain networks (i.e., default mode network). pCASL quantifies regional cerebral blood flow using magnetically labeled blood water content and will serve as a marker of resting state cerebral perfusion that has also been shown to correlate with regional brain metabolism and levels of neuronal activity.

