3. SPECIFIC AIMS

3.1 Overall Study Design and Plan

The study uses a double-blinded, placebo lead-in, randomized, parallel group, PBO-controlled design. For this clinical trial, one-hundred individuals over 17 years of age meeting operationalized criteria for Long-COVID will be recruited. These 100 participants will undergo a placebo lead-in period of two weeks. Sixty participants will then be randomized to NR (TruNiagen®, Chromadex) 1000 mg twice daily for 22 weeks, and 40 will receive placebo for the next 10 weeks followed by NR for 10 weeks. Outcomes will consist of standardized cognitive, neuropsychiatric, physical, functional and biomarker assessments as well as daily sleep and activity monitoring with wearable actigraphy.

Randomized, Placebo-Controlled Parallel Group Clinical Trial of Nicotinamide Riboside to evaluate NAD+ Levels in Individuals with Persistent Cognitive and Physical Symptoms After COVID19 Illness ("Long-COVID")

Version 1.1

The study will also help better understand the nature of long-COVID by comparing this group with a healthy control group of individuals who were infected with COVID-19 but fully recovered. To better address this aim, we will also increase our sample size of individuals with long-COVID by testing individuals with long-COVID ages 18 and older who will only complete 1 visit. Comparing these groups will help establish differences in NAD+ levels at baseline associated with long-COVID, as well as help elucidate the cognitive profile, neuropsychiatric and physical functioning, and markers of glia and neural functioning in this population. Participants in these additional cohorts will only complete one visit and will not be administered NR or PBO.

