9.1 Primary analysis

For all outcomes, we will perform intention-to-treat (ITT) analysis and mixed-effects model repeated measures (MMRM). Group (NR-NR vs. PBO-NR sequence), time, and group by time interactions will be included in the MMRM as fixed effects. The study's outcomes will be the change score of ECog, RBANS, and TMT-B from baseline, and the change in NAD+ levels from baseline. We also will examine changes in the FSS, BAI, BDI, and PSQI scores. An unstructured covariance matrix will be used to account for the correlation of repeated measures within a participant. Age, sex, and education will be included in the models as covariates.

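### Sections 3.2.1 and 9.1 list different primary outcomes, and no contrast, visit, alpha or multiplicity rule says which test decides the trial

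*Combined protocol and SAP*

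**What the plan says.** Section 3.2 sets one primary objective: "To measure the effect of NR vs PBO on standard assessments of cognition and subjective cognitive concerns". Section 3.2.1 turns it into outcomes: "The primary outcome of this study will be objective measures of cognitive performance and subjective cognitive concerns measured with the following tests". The tests are MMSE, Digit Span backwards, RBANS, TMT, D-KEFS Verbal Fluency, CPT, BRIEF-A and ECog, and none is ranked.

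Section 9.1 first applies ITT and an MMRM to every outcome. It then states: "The study's outcomes will be the change score of ECog, RBANS, and TMT-B from baseline, and the change in NAD+ levels from baseline". A further sentence adds: "We also will examine changes in the FSS, BAI, BDI, and PSQI scores". On the model it says: "Group (NR-NR vs. PBO-NR sequence), time, and group by time interactions will be included in the MMRM as fixed effects".

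NAD+ enters Section 3.2.1 outside the primary list, where the plasma assays are described ("as well as NAD+/NADH"). Section 3.2 makes plasma markers of metabolic target engagement an exploratory objective.

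On the design, Section 3.1 says of the comparison arm: "40 will receive placebo for the next 10 weeks followed by NR for 10 weeks".

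**The concern.** Two sections define what the trial is judged on, and they differ. A reader of 3.2.1 expects eight primary instruments. A reader of 9.1 expects three, with NAD+ beside them. Section 9.1 does not call its three outcomes primary (only the section heading does), and it does not say whether the other five keep that status.

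Nothing else in the statistical section settles the matter. It names no lead test, contrast, visit, significance level, multiplicity rule or success criterion. The choice of score within RBANS and ECog is also open.

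The contrast matters because of the design. Once the placebo arm moves to NR, a difference between the two sequences no longer compares NR with placebo. A model containing group, time and their interaction can yield several different tests, and the plan does not say which one answers the primary objective. At stake is whether a positive result could be read as confirmatory, or only as one of several unadjusted tests.

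**Working it through.** The plan states no alpha, power or error rate, so there is no figure to reproduce. The contents page lists a sample size section under 9.1, but the body has none.

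**Step 1: compare the lists.** Section 3.2.1 has 8 instruments. Section 9.1 has ECog, RBANS and TMT-B, so 3 of the 8 (TMT-B being one part of the TMT), plus NAD+. Not named in 9.1: MMSE, Digit Span backwards, D-KEFS Verbal Fluency, CPT and BRIEF-A, so 8 − 3 = 5.

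**Step 2: scores within instruments.** Section 7.1.2.2.2 describes five RBANS domains from twelve subtests. Section 7.1.2.2.6 describes a global ECog factor and six domain factors. Section 9.1 selects none of them.

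**Step 3: visits** (Sections 3.1, 3.2.1, 6.1, 6.2.3, 7.1.2.2.2).

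| Outcome | Post-baseline visits | Of these, NR vs placebo |
|---|---|---|
| RBANS, TMT-B | Weeks 12, 22 | Week 12 |
| ECog | Weeks 7, 12, 17, 22 | Weeks 7, 12 |

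Week 12 is the only placebo-controlled visit common to all three. A group main effect, a joint group-by-time test or a Week 22 difference would all fit the model in 9.1, and each uses visits at which both arms take NR.

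**Step 4: chance of at least one false positive.** Assumptions, because the documents give none: two-sided 0.05 per test, no true effect, and any one significant test counts as success. NAD+ is left out because Sections 2.1.4 and 2.1.5 lead one to expect a rise.

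For independent tests the chance is 1 − (1 − 0.05)^k:
- k = 3: 1 − 0.95³ = 14.3%
- k = 8: 1 − 0.95⁸ = 33.7%

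Counting only errors in favour of NR, it is 1 − (1 − 0.025)^k:
- k = 3: 7.3%
- k = 8: 18.3%
- k = 1: 2.5%

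For correlated tests, equicorrelated normal statistics were simulated with 1,000,000 draws and a cut-off of 1.96:

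| Correlation | 0 | 0.3 | 0.5 | 0.7 | 0.9 |
|---|---|---|---|---|---|
| 3 tests, either direction | 14.3% | 13.6% | 12.5% | 10.9% | 8.3% |
| 3 tests, favouring NR | 7.3% | 6.8% | 6.3% | 5.5% | 4.2% |
| 8 tests, either direction | 33.7% | 30.0% | 25.0% | 19.2% | 11.9% |
| 8 tests, favouring NR | 18.3% | 15.2% | 12.5% | 9.6% | 6.0% |

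**Step 5: dependence on the success rule.** If all three outcomes had to succeed, the rate would be 0.05³ = 0.01% at correlation 0, 0.3% at 0.5 and 0.9% at 0.7. The error rate therefore depends on a rule that the plan does not state.

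**Step 6: cost of Holm across three.** The first step uses 0.05/3 = 0.0167. With 60:40 all analysed and no gain from covariates, the effect detectable with 80% power is approximately (z for alpha + 0.842) × √(1/60 + 1/40), where the root is 0.204.
- Alpha 0.05: (1.960 + 0.842) × 0.204 = 0.57 SD; noncentral t gives 0.58.
- Alpha 0.0167: (2.394 + 0.842) × 0.204 = 0.66 SD; noncentral t gives 0.67.

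Power for a 0.58 SD effect at that step falls from 80% to 66%. With an assumed 15% dropout (51:34), the detectable effect rises from 0.63 to 0.73 SD.

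**The case against.** Several replies have force.

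- **The deciding visit can be worked out.** The objective is NR versus placebo and placebo stops at Week 12, so a Week 22 difference could not answer it. This stands as an inference. A reader might conclude that the plan allows the primary claim to rest on Week 22, but Section 3.2 does not support that. What remains is that 9.1 names no contrast, and ECog has two eligible visits.
- **The other five instruments are not dropped.** The opening sentence of 9.1 can be read as extending the model to them. That is a fair reading, but it does not say whether they are still primary.
- **NAD+ has a stated tier.** The running title ("Clinical Trial of Nicotinamide Riboside to evaluate NAD+ Levels in Individuals with Persistent Cognitive and Physical Symptoms") and 9.1 might suggest that a rise in NAD+ alone could count as success. Sections 3.2 and 3.2.1 place it outside the primary tier, and the primary objective concerns cognition only. The defect is a conflict with 9.1, not a missing tier.
- **FSS, BAI, BDI and PSQI are tiered elsewhere.** Sections 3.2 and 3.2.1 put them below the primary objective, so 9.1 need not repeat it.
- **The error rates are assumed.** True. It is tempting to quote 34% as the trial's false-positive rate, or a higher figure from testing every visit separately. The first needs eight independent tests with any one sufficing. The second is not what 9.1 describes, which is a repeated-measures model.
- **The objective is to measure an effect, with no success criterion, so strict error control is a design choice.** This is partly right. The protocol nevertheless declares a primary objective, outcome and analysis, so the lists must agree and the contrast must be named under any philosophy.

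**Conclusion.** The point holds. Sections 3.2.1 and 9.1 disagree on the primary outcome, 9.1 places an exploratory biomarker beside the cognitive tests, and no rule identifies the deciding test. Following 9.1 as written means several unadjusted tests under a primary heading.

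Under the Step 4 assumptions, the either-direction error exceeds 5% at every correlation examined, for three tests and for eight. False claims favouring NR run at about 7% to 4% and 18% to 6%, against 2.5% for one test. These figures illustrate the size and are not properties of the plan, which gives no alpha, success rule or correlation.

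The documents do not show that the plan intends a Week 22 comparison, that NAD+ could meet the primary objective, or that five instruments have been abandoned. This is a correction that should be made, and it does not invalidate the design.

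**What to change.** Before database lock and the release of treatment codes (Section 9.1.3):

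1. Make the primary lists in 3.2.1 and 9.1 agree, for example on ECog, RBANS and TMT-B, with one named score each for RBANS and ECog. The documents do not say which list governs, so the choice is the sponsor's.
2. Define the primary contrast as the NR versus placebo difference in change from baseline at Week 12, estimated from the MMRM.
3. State an overall two-sided 5% level, with either one single primary outcome or Holm across the three.
4. Label the remaining 3.2.1 instruments secondary.
5. In 9.1, label NAD+ as exploratory target engagement, in line with 3.2 and outside the cognitive family.

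The cost is wording in two sections, with no new data or visits. Holm carries the loss of sensitivity shown in Step 6. A single primary outcome avoids that loss, but the other two outcomes could then not carry the primary claim.

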2.1.4 Pharmacokinetics of Nicotinamide Riboside in Humans

An open-label, non-randomized study of the pharmacokinetics of NR carried out at the University of Washington demonstrated both the impact of NR on NAD⁺ levels in humans and its tolerability¹⁶. Eight subjects underwent dose escalation from 250 mg of NR twice daily to 1000 mg of NR twice daily over the course of nine days, with NR and NAD⁺ levels determined at baseline Day 1 and over the course of a 24-hour pharmacokinetic study on Day 9. No adverse events were reported in clinical laboratory values, including potassium, which had been noted to be elevated in previous NR studies. Slight, but significant decreases in hematocrit, hemoglobin, and platelet count were reported. All but one subject showed an increase in blood NR levels from baseline to Day 9, ranging from 10% to 127% increases. Blood NR showed exponential decline from 3 to 12 hours with a half-life of 2.7 hours. Despite relatively fast clearance of NR, blood NAD⁺ levels were significantly increased to steady state (see Figure 3) by 35 to 168% from baseline. NR treatment did not produce side effects commonly seen in niacin treatment, such as flushing, pruritus, hyperglycemia, hyperuricemia, or elevation of liver or muscle enzymes. However, a variability in NR bioavailability was observed, suggesting that NR relies on active transport across intestinal mucosa, which can vary highly from person to person.

Randomized, Placebo-Controlled Parallel Group Clinical Trial of Nicotinamide Riboside to evaluate NAD+ Levels in Individuals with Persistent Cognitive and Physical Symptoms After COVID19 Illness ("Long-COVID")

Version 1.1

[figure not shown]

Figure 3. Blood NR and NAD⁺ levels in n = 8 subjects following NR dose escalation from 250 to 1000 mg twice daily.⁶

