7.1.2.5 Magnetic Resonance Imaging (MRI)

Subjects will be given the opportunity to participate in an optional MRI sub-study at Baseline (Week 0) and End of Study (Week 22). Subjects in the healthy control group will complete the MRI at their one-time visit. Subjects electing to participate will be asked to complete both MRIs to be part of the sub-study. Data will be collected on a 3-Tesla Siemens scanner with the following scan sequences: a high resolution T1-weighted scan, T2 FLAIR, resting state BOLD MRI, and pCASL at rest.

Resting state BOLD measures low-frequency spontaneous fluctuations in BOLD signal across time, where correlations of this spontaneous activity between brain regions are thought to reflect functional connectivity. The 10-minute rsfMRI scan will be acquired with whole-brain echo planar imaging (EPI) time series with a voxel size of 2x2x2 mm isotropic, TR/TE = 4000/30 ms, acquisition matrix = 64x64, and 40 axial slices. Subjects will be instructed to keep their eyes open throughout the duration of the scan. rsfMRI data will be processed within the FreeSurfer FS-FAST stream using standard pre-processing steps including motion correction, masking of non-brain tissue, registration to the anatomical high-res image, sampling to the surface, and surface smoothing by 5 mm. Temporal filtering to extract signals in the 0.008-0.08 Hz frequency band will be performed, followed by linear regression to factor out mean global signal, average signal from white matter, and average signal from ventricular cerebrospinal fluid (CSF) regions. To perform functional connectivity analyses, we will use a seed-based approach to examine temporal correlations between the mean time course within anatomically-defined nodes and the rest of the brain.

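### The scheduled MRI times (Week 2 and Week 22) give no randomised NR-versus-placebo imaging contrast, because the placebo arm starts NR at Week 12

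*Combined protocol and SAP*

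**What the plan says.** Section 3.2 lists an exploratory objective: "To measure the effects of NR on cerebral neurophysiology (in an optional sub-study) using resting state functional magnetic resonance imaging (rs-fMRI"), with connectivity measured by resting-state BOLD. Section 3.2.1 adds arterial spin labelling (perfusion) to each session and fixes the times: "Optional MRI will be conducted at two time points: Week 2 and End of Study (Week 22"). The visit lists agree. An optional scan appears at Baseline (6.2.2) and at the final visit (6.2.4), but not at Weeks 7, 12 or 17 (6.2.3). Section 6.2.5 also offers an optional scan at the Early Termination visit.

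On treatment, Section 3.1 says of the smaller arm that "40 will receive placebo for the next 10 weeks followed by NR for 10 weeks". Figure 4 (Section 5.3) and Section 9.1.2 place that switch at visit 2, Week 12.

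Section 4.2 caps the repeat-scan sub-study at 24 completers. Section 9.1 applies the mixed model to all outcomes, comparing the two sequences, but names no MRI outcome.

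Section 7.1.2.5 dates the scans differently: "Baseline (Week 0) and End of Study (Week 22").

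**The concern.** A placebo arm lets a change after NR be set against the change that would have occurred anyway. People with long COVID may improve over five months, may respond to taking a capsule, and may scan differently the second time. Imaging is scheduled once before any NR and once when both arms are taking it, so the placebo phase passes without a scheduled follow-up scan. A change in connectivity or perfusion at Week 22 could then be reported as an effect of NR when the design cannot tell it from these other causes. Conversely, an absence of difference between arms at Week 22 could be read as absence of effect when both arms had responded fully.

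**Working it through.** **Inputs.** Scan times are from 3.2.1, 6.2.2 and 6.2.4. The switch at Week 12 is from 3.1, 5.3 and 9.1.2. Allocation is 60:40 (3.1), with 24 repeat-scan completers (4.2). The documents give no alpha, power, effect size or SD for imaging, so there is no planned figure to reproduce. I assume two-sided alpha 0.05, 80% power, effects in SD units of the change score, and a split following 60:40: 24 × 0.6 = 14.4 and 24 × 0.4 = 9.6, taken as 14 and 10.

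**Step 1: cumulative NR exposure at each time.**

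| Time | NR-NR | PBO-NR | Scheduled MRI |
|---|---|---|---|
| Week 2 | 0 weeks | 0 weeks | yes |
| Week 12 | 10 weeks | 0 weeks (placebo) | no |
| Week 22 | 20 weeks | 10 weeks | yes |

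The 20 weeks is the interval between the Week 2 and Week 22 visits. Section 3.1 says 22 weeks for this arm. The two need reconciling, but the argument is the same either way.

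**Step 2: what each contrast estimates.** Let E(t) be the effect of t weeks of NR, and N(t) everything else that changes over t weeks after baseline (recovery, placebo response, repeat scanning, drift). Assume N is common to the randomised arms.

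- Week 22: NR-NR change = E(20) + N(20). PBO-NR change = E(10) + N(20). Difference = E(20) − E(10).
- Week 12, if scanned: NR-NR change = E(10) + N(10). PBO-NR change = N(10). Difference = E(10).

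At Week 22 randomisation removes N, but also removes the first 10 weeks of effect. The within-arm change keeps the effect, but also keeps N(20).

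**Step 3: what is left at Week 22.** The table shows the contrast as a share of E(10), and the chance of p < 0.05 by two-sample t-test (14 vs 10) if E(10) = 0.8 SD. The shapes and the 0.8 SD are assumptions. For an exponential approach with time constant τ weeks, the share is exp(−10/τ).

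| Shape of E(t) | [E(20) − E(10)] / E(10) | Week 22 | Week 12 |
|---|---|---|---|
| Plateau by 10 weeks | 0% | 5% (alpha only) | 46% |
| Exponential, τ = 5 | exp(−2) = 14% | 6% | 46% |
| Exponential, τ = 10 | exp(−1) = 37% | 10% | 46% |
| Linear to 15 weeks, then flat | (1.5 − 1)/1 = 50% | 15% | 46% |
| Linear to 20 weeks | (2 − 1)/1 = 100% | 46% | 46% |

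Week 22 beats Week 12 when E(20) − E(10) > E(10), that is, when E(20) > 2 × E(10). This requires an effect that accelerates or starts late.

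**Step 4: precision.** The normal approximation to the detectable difference is (1.96 + 0.84) × √(1/14 + 1/10) = 2.80 × 0.414 = 1.16 SD. The t-test with 22 degrees of freedom gives 1.21 SD. An uneven uptake of the optional scans changes this little: 1.20 SD at 12:12 and 1.38 SD at 18:6 by the same t calculation.

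**Step 5: do other parts of the plan supply the contrast?**

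- The mixed model in 9.1 compares sequences, so for Week 22 imaging it estimates E(20) − E(10).
- The pooled analysis in 9.1.2 looks at change after 5 and 10 weeks of NR. There is no 5-week scan, the NR-NR arm has no 10-week scan, and the PBO-NR change spans 10 weeks of placebo plus 10 of NR.
- Healthy controls are scanned once, so they carry no information on change.
- Participants with a baseline scan only (up to 50 more, Section 4.2) likewise carry none.

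**The case against.** Several points on the other side stand.

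- **The objective does not promise a placebo comparison.** The primary objective is worded "To measure the effect of NR vs PBO on standard assessments of cognition and subjective cognitive concerns"; the imaging objective says only "To measure the effects of NR on cerebral neurophysiology". A reader might infer that the sub-study cannot answer its objective at all. The text does not support that: a randomised comparison of longer with shorter exposure remains, and so does a within-person change. Both are weak, but weak is not empty.
- **Some placebo-phase scans are possible.** A reader might infer that nobody can be scanned after baseline while on placebo. Section 6.2.5 allows an optional scan within 7 days of stopping treatment, so a PBO-NR participant who withdraws before Week 12 could supply one. Such participants are self-selected and no comparison is planned for them, so this does not repair the design.
- **An early plateau is not shown.** Section 2.1.4 reports that blood NAD+ "levels were significantly increased to steady state (see Figure 3) by 35 to 168% from baseline", but in eight subjects over nine days. It says nothing about when brain connectivity or perfusion would level off. The plateau is a scenario the design should withstand, not an established fact.
- **Week 12 is not better under every shape.** With delayed onset (E(20) more than twice E(10)), the Week 22 contrast is the larger one. The documents do not exclude this.
- **The stakes are limited.** The sub-study is optional and exploratory. Even at Week 12, power for 0.8 SD is below one half. The primary and secondary outcomes, and the cross-sectional comparison with healthy controls, are untouched.

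None of this creates a scheduled NR-versus-placebo scan.

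**Conclusion.** The point holds in this form: the scheduled MRI times contain no randomised NR-versus-placebo contrast. Week 22 compares about 20 with 10 weeks of NR, and that difference ranges from 0% to 100% of the 10-week effect across the shapes examined, being near zero if the effect plateaus by 10 weeks. The within-person change is confounded with recovery, placebo response and repeat scanning. That much follows from the schedule. The percentages rest on assumed effect shapes, and the power and detectable-difference figures also on a 14:10 split and conventional error rates.

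The stated objective names connectivity only. Perfusion is an outcome measure in 3.2.1, so the same limit applies to it, but it should not be described as part of the objective.

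This is a worthwhile improvement to an exploratory sub-study, not a threat to the trial's main conclusions. The Week 0 label in 7.1.2.5 is a separate editorial inconsistency. Both dates precede NR, so it does not affect the argument.

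**What to change.** Move the repeat MRI of the 24-participant sub-study from Week 22 to the Week 12 visit, and require it before the PBO-NR arm takes its first NR. State the analysis: between-arm difference in change from Week 2, with its confidence interval, labelled exploratory.

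**Cost.** This needs a protocol and consent amendment, changes to the visit lists in 6.2.3 and 6.2.4, and provision for the Week 12 visit to spread over more than one day, as 6.2.2 already allows at Baseline. The number of scans is unchanged, and the cognitive battery is already given at Week 12. The 20-week image is lost, and an effect that emerges only after 10 weeks would be missed. The move restores a controlled comparison but not precision, which stays at about 1.2 SD.

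**If both times matter**, scan at Weeks 2, 12 and 22. That adds up to 24 scans, or 24 × $100 = $2,400 in participant payments at the rate in 5.2, plus scanner time, for which the documents give no cost.

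**If Week 22 alone is kept**, say in 3.2 and Section 9 that imaging will be reported as an uncontrolled pre-post change plus a contrast of longer with shorter NR exposure, and that change will not be attributed to NR.

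**Separately**, reconcile the Week 0 baseline scan in 7.1.2.5 with Week 2 in 3.2.1 and 6.2.2, and the 22 weeks of NR in 3.1 with the 20 weeks between the Week 2 and Week 22 visits.
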